## Background of the Project including Preliminary Observations

---

Describe the relevant background of the proposed study. Discuss the previous related works on the subject by citing specific references. Describe logically how the present hypothesis is supported by the relevant background observations including any preliminary results that may be available. Critically analyze available knowledge in the field of the proposed study and discuss the questions and gaps in the knowledge that need to be fulfilled to achieve the proposed goals. Provide scientific validity of the hypothesis on the basis of background information. If there is no sufficient information on the subject, indicate the need to develop new knowledge. Also include the **significance and rationale** of the proposed work by specifically discussing how these accomplishments will bring benefit to human health in relation to biomedical, social, and environmental perspectives. (DO NOT EXCEED 5 PAGES. USE CONTINUATION SHEETS).

---

Malnutrition of under-5 children is a major health problem of the developing countries [1] and is associated with 54% of all deaths in this age group [2]. Death rates among severely malnourished children have remained almost unchanged over the last five decades, and are as high as 49% even during the 1990s [3]. This signifies inadequacies/ineffectiveness of programmes to address this issue.

About 94% of under-5 children in Bangladesh suffer from malnutrition of one kind or another, and about 66% of the children are stunted and 15% are wasted [4]. Thus, malnutrition has been correctly identified as the "silent emergency" in Bangladesh [5]. Malnutrition not only causes a short stature and reduced physical output, but when occurs early in life is often associated with impaired development of brain which is irreversible unless efficiently corrected. Thus, there is an increasing concern about the future intellectual potentials of Bangladesh.

The current management and/or rehabilitation of severely malnourished children is heavily dependent on expensive hospital- or nutritional rehabilitation unit (NRU)-based care where, most often, children are brought for other acute medical problems. There are only a few nutritional rehabilitation units in the city of Dhaka which is populated by nearly 10 million people- about 1/12th of the entire country, with a much fewer-than-required beds. Logically, therefore, such hospital/health care centre-based programmes are not likely to make any significant improvement of the ever pervasive problem of malnutrition in Bangladesh.

Most residential NRUs require that the mothers remain with their children, while the day care centres require that the mothers bring their children and take them home on a daily basis. Since most mothers have other family commitments including taking care of other children, while some mothers may have occupational problems, and day care strategies may require travelling a long distance often involving a substantial amount of money, such programmes fail to meet the specific requirements of the target group. Consequently, dropout rates from such programmes are also very high. This requires development of a programme which is effective, sustainable, likely to be acceptable to all mothers, and cost-effective.

For a successful nutritional rehabilitation programme it is very important to identify and effectively treat acute medical conditions that not only accompany such children but are also the principal reasons for taking them to a health-care facility. Nutritional rehabilitation involves provision of high calorie food containing adequate amounts of protein. On the other hand, in determining the optimal food for nutritional rehabilitation of severely malnourished children, it is also important that the food be inexpensive, easy to prepare, culturally acceptable to mothers and

children, and the ingredients are locally available. *Khichuri* and *halwa* (appendix 1) are examples of such diets developed for severely malnourished children at the ICDDR,B with optimum amount of ingredients, and are being used successfully in nutritional rehabilitation [6]. *Khichuri* is an energy-dense diet prepared from rice, soya oil, vegetables, and lentils while *halwa* is a more energy-dense sweet diet made from rice flour, soya oil, lentils, and molasses. Both the diets provide energy as well as protein from vegetable sources that are inexpensive and easily available.

The Clinical Research and Service Centre (CRSC) of the ICDDR,B (popularly known as the "Cholera hospital") currently treats around 115,000 patients each year and about 60% of them are under-5 children. Nearly 80% of all children (about 5,500 children) requiring treatment in the inpatient units for a longer period of time (median period of stay, 4.5 days) suffer from severe malnutrition. After recovering from diarrhoea and associated medical problems, a few of them (due to bed constraints and refusal of mothers to stay in the hospital for a longer period of time) undergo nutritional rehabilitation in the NRU run by the Child Health Programme of the CRSC. The NRU has only 16 beds where the very severely malnourished children are admitted with their mothers, treated for a period of 15-30 days, and discharged when their WH exceeds 80%, they are free of oedema, and have a good general condition. The number of beds in the NRU is clearly far less than what is required. On the other hand, a large number of mothers refuse to stay in the NRU for a long period of time because of family commitments at home. A survey done in January-May 1998 revealed that among 340 severely malnourished children eligible for admission to the NRU of the CRSC, mothers of only 142 children (42%) agreed to have their children admitted to the NRU. Children who cannot be accommodated in the NRU or those who refuse to stay for a prolonged period of time in the NRU are advised to come for follow-up at regular intervals. However, the follow-up rates have always been sub-optimal.

Community-based management of severely malnourished children has rarely been considered and tested in a methodical way [7]. However, in a study performed in Dhaka, home management of severely malnourished children after 7 days of inpatient care was found to be a cost-effective method of nutritional rehabilitation [8]. This study was done on children who were more than 12 months of age. Of 1332 children treated during the study period, 759 (57%) children were not recruited into the study because of age being less than 12 months (398), critical illness or severe anaemia (243), tuberculosis or other disease (108), or distance (10). The mean weight gain was only 4 g/kg body weight per day. Therefore, after treatment of the acute illness and an initial 7-day period of NRU care, the efficacy of defined low-cost diets including *khichuri* and *halwa* in the home management of severely malnourished younger children presenting with acute illness (with follow-up at outpatient clinic or at home) needs to be assessed. In this context, it is pertinent to mention here that in an earlier study involving the acute phase management of severely malnourished children at the ICDDR,B hospital at Dhaka, the median age of children was 6.5 months, 60% of whom had pneumonia and 30% had clinically diagnosed septicemia [9].

## Significance

The proposed study will investigate the effectiveness of home-based nutritional rehabilitation (with follow-up at outpatient clinic or at home) using indigenous, low-cost diets compared to hospital-based treatment of severely malnourished children recovering from diarrhoea and other

acute illness(es). It attempts to find an inexpensive, participatory and sustainable alternative to expensive hospital-based nutritional rehabilitation.

## Rationale

- If the hospital to home-based nutritional programme is found to be more cost-effective than the hospital-based programme, then it will be possible to rehabilitate more severely malnourished children with the same amount of available resources.
- It will be possible to extend the programme, if found to be effective, to other locations/health centres on a country-wide basis through governmental and non-governmental health care services.
- Home visits will provide health and nutrition education to the study mothers as well as neighbouring mothers, will help in the identification of medical problems and early referral of sick children to appropriate health centres.
- Active participation will help in confidence building of mothers on home management of severely malnourished children. Preparation and use of low-cost diets will help in preventing malnutrition among siblings as well as in subsequent children.

## Research Design and Methods

---

Describe in detail the methods and procedures that will be used to accomplish the objectives and specific aims of the project. Discuss the alternative methods that are available and justify the use of the method proposed in the study. Justify the scientific validity of the methodological approach (biomedical, social, or environmental) as an investigation tool to achieve the specific aims. Discuss the limitations and difficulties of the proposed procedures and sufficiently justify the use of them. Discuss the ethical issues related to biomedical and social research for employing special procedures, such as invasive procedures in sick children, use of isotopes or any other hazardous materials, or social questionnaires relating to individual privacy. Point out safety procedures to be observed for protection of individuals during any situations or materials that may be injurious to human health. The methodology section should be sufficiently descriptive to allow the reviewers to make valid and unambiguous assessment of the project. (DO NOT EXCEED TEN PAGES, USE CONTINUATION SHEETS).

---

### Study Design

Prospective and randomized, clinic to community study

### Enrollment Criteria

Age:	6 months to 5 years
Gender:	Either
Nutritional status:	Severely malnourished (WH < 70% of the NCHS median or with oedema)
General condition:	Resolution of acute illness including diarrhoea, pneumonia, gross electrolyte imbalance, and septicemia. Criteria of resolution of acute illnesses are outlined under management of acute illness .
Place of residence:	Within 10 km from the CRSC (for convenience of follow-up)

## Exclusion Criteria

- Informed consent: Failure to obtain informed consent from parents or caretakers  
Address: Children without any fixed address  
Medical conditions: Children with tuberculosis or any congenital/acquired disorder affecting growth i.e. trisomy-21 or cerebral palsy; children on an exclusion diet for the treatment of persistent diarrhoea.

## Interventions

Upon resolution of the acute illness, eligible children will be randomized to receive any of the three following interventions:

1. Home-based nutritional rehabilitation with home follow-up (treatment A, n=75)
2. Home-based nutritional rehabilitation with outpatient follow-up (treatment B, n=75)
3. Hospital-based nutritional rehabilitation (treatment C, n=75).

## Randomization

Randomization will be performed according to a random numbers table using permuted blocks of variable lengths.

## Patient Management

### Management of Acute Illness

As the children will be acutely ill with diarrhoea and other complicating illnesses including pneumonia, electrolyte imbalance, or septicemia, they will be treated in the inpatient units according to the standardized management protocol now being used in the CRSC. Implementation of this protocol resulted in a 47% reduction in mortality during the acute phase of treatment of severely malnourished children with diarrhoea admitted to the CRSC [9]. Duration of, and management provided during the acute phase of treatment will be recorded. Upon resolution of the acute illness, children will be randomized to receive any of the three interventions for nutritional rehabilitation and transferred to the NRU.

Criteria of resolution of acute illnesses are:

- Diarrhoea: No watery or liquid stools during the last 24 hours, no signs of dehydration, absence of blood or excessive mucus in stools.
- Pneumonia: No fast breathing (respiratory rate  $\leq 50$ /min in a child  $< 1$  year,  $\leq 40$ /min for a child  $\geq 1$  year of age), no chest indrawing, no wheeze, no cyanosis, able to drink, reduction in crepitations compared to admission auscultation.
- Electrolyte imbalance: Absence of lethargy or head lag, no irritability or fast breathing.

Septicemia: No signs of circulatory collapse (cold hands and feet, weak radial pulse, not alert), conscious, normal body temperature.

In addition, a child should be hungry and should not require a nasogastric tube for feeding.

### **Treatment A**

In this treatment schedule, children will stay in the NRU for 7 days during which period their clinical condition will stabilise, and their mothers or caretakers will have learnt preparation of khichuri and halwa and taking care of the children at home. Thereafter, they will be discharged and health workers will visit them at their homes at regular intervals until they achieve a WH >80%, are free of oedema, and have a good general condition. If a child develops an acute illness or the general condition is not satisfactory at the time of discharge, then the discharge will be postponed till resolution of the illness. During stay in the NRU, calories and protein are gradually increased over a period of time in a programmed way in order to achieve rapid growth involving a weight gain of more than 10 g/kg per day. A major element of the method of nutritional rehabilitation practised in the NRU of the CRSC is that the diet given to the children contains proteins derived mainly from vegetable sources. Food containing animal protein such as milk (which is given only initially), eggs, meat or fish are expensive, and the mothers of these children can hardly afford these foods when continuing nutritional rehabilitation at home.

The diet schedule to be followed for the children is as shown on the following page. This is the standardized diet schedule that is currently being routinely practiced in the NRU of the CRSC.

Diet	Item & amount	Energy intake Kcal/kg.day	Protein intake g/kg.day
1	Milk suji 10 ml/kg.feed (110ml/kg.day) 2 hrly (11 feeds per day)*	74	1.5
	Halwa 10 g/kg.feed 2 feeds per day	48	1.0
	Total:	122	2.5
2	Milk suji 10 ml/kg.feed (110ml/kg.day) 2 hrly (11 feeds per day)*	74	1.5
	Halwa 10 g/kg.feed 2 feeds per day	48	1.0
	Khichuri 10 g/kg.feed 2 feeds per day	29	0.6
	Total:	151	3.1
3	Milk suji 100 10 ml/kg.feed (110ml/kg.day) 2 hrly (11 feeds per day)*	110	2.8
	Halwa 10 g/kg.feed 2 feeds per day	48	1.0
	Khichuri 10 g/kg.feed 2 feeds per day	29	0.6
	Total:	187	4.4
4	Milk suji 100 10 ml/kg.feed (110ml/kg.day) 2 hrly (11 feeds per day) *	110	2.8
	Halwa 10 g/kg.feed 3 feeds per day	72	1.5
	Khichuri 10 g/kg.feed 3 feeds per day	43	0.9
	Total:	225	5.2
5	Milk suji 100 10 ml/kg.feed (40ml/kg.day) 6 hrly (4 feeds per day)	40	1.0
	Halwa 20 g/kg.feed 3 feeds per day	144	3.0
	Khichuri 20 g/kg.feed 3 feeds per day	87	1.8
	Total:	271	5.8

\* There is a gap in feeding at 4 a.m. Composition of milk suji and milk suji 100 (appendix 2)

Diets 1, 2, 3 and 4 will be provided on days 1, 2, 3 and 4 respectively. These diets ensure 2 hourly feeds with milk suji at least for the first 4-5 days of nutritional rehabilitation. Diet 5 is started when the child achieves an intake of 225 kcal/kg per day, which is possible by day 7. Most of the calorie and protein in diet 5 are derived from halwa and khichuri, the number of milk feeds being only four per day. The child will be given plain water in between the feeds, and breast feeding continued if applicable. The amount of each feed offered and actually taken will be recorded on a feeding chart. Upon discharge, the mother or caretaker will be advised to prepare khichuri and halwa at home and feed the child specified amounts or more for further nutritional rehabilitation. A plastic cup and a spoon will be provided to each child, but ingredients for khichuri and halwa will not be provided. A health worker will calculate the specified amounts of khichuri and halwa using a chart (appendix 3) and instruct the mother regarding the minimum number of cups of the diets to be given to the child each day.

**Micronutrient Supplementation:** If there is no xerophthalmia, vitamin A as a single dose will be given 200,000 units above 1 year of age, and 100,000 U for infants 6-12 months. If the child has xerophthalmia, the course of vitamin A will be completed. Zinc acetate syrup, multivitamin drops and folic acid will be provided by the health worker till the child achieves an oedema-free WH >80%. Elemental zinc will be given in a dose of 2 mg/kg per day. Multivitamin drops will be provided 1 ml twice daily if age > 1 year, 1/2 ml twice daily if age < 1 year. One ml of commercially available multivitamin drops contains vitamin A (as palmitate) 5,000 IU, vitamin D 1,000 IU, thiamine hydrochloride 1.6 mg, riboflavin 1 mg, pyridoxine hydrochloride 1 mg, nicotinamide 10 mg, calcium D-pantothenate 5 mg, and ascorbic acid 50 mg. Folic acid will be given 1.25 mg (one-fourth of a tablet) once daily. Potassium chloride syrup will be provided 4 mmol/kg per day three times daily for 5 days. Iron supplementation will be started from the *second week* of treatment and continued for 2 months. The dose is 3 mg of *elemental* iron/kg per day given once daily between meals (one tablet of *Folfe* contains 65 mg elemental iron). Children weighing 4-6 kg will be given one-fourth of a tablet *Folfe* once daily, those weighing >6 kg given one-half of a tablet. Since iron and zinc interfere with the absorption of each other, mothers will be instructed not to give these micronutrients at the same time.

**Training of Mothers or Caretakers:** During the 7 day stay in the NRU, mothers or caretakers will be given structured lessons on the causes and prevention of malnutrition, preparation of nutritious low-cost diets including halwa and khichuri, the need for emotional and physical stimulation of the child, home management of diarrhoea, how to recognise symptoms of common illnesses such as pneumonia and when to seek help, and counselling about birth spacing. This will enable them to continue care and proper feeding of the child after discharge from the NRU and also to prevent malnutrition in siblings and in subsequent children. They can also spread the knowledge acquired to other mothers in the community.

**Immunization:** Children who have not been immunized earlier will be given vaccines as per the Expanded Programme on Immunization guidelines.

**Anti-helminthic treatment:** Children >1 year of age will be given mebendazole, 100 mg two times daily for 3 days, if such treatment has not been provided in the last six months. This treatment will be provided after two weeks of nutritional rehabilitation.

**Follow-up:** After the child is discharged from the NRU, a health worker will visit the child every week for one month and then at fortnightly intervals until the child achieves an oedema-free WH >80%. During each visit, the child's general condition will be assessed, weight and height (or length) measured, presence or absence of oedema noted, supplies of micronutrients provided, compliance of feeding and micronutrient supplementation checked by 24 hours recall, and morbidity recorded, if any. To aid recall of morbid conditions, on each visit mothers will be given a pictorial calendar portraying a well child and children with diarrhoea, vomiting, cough, fever, eye infection, or discharging ears [10]. Mothers will be requested to record daily on the calendar whether the condition had been present or absent in the previous 24 hours. Morbidity will then be recorded on a precoded form with the help of the calendar. Diarrhoea will be defined as the passage of three or more watery or liquid stools per day. An episode will be considered new if at least two diarrhoea-free days intervene between the present and previous episodes. The health worker's identification of children with pneumonia of different grades of severity will be based upon WHO guidelines [11]. Lack of weight gain for two consecutive visits will constitute failure to respond. The health worker will refer to the CRSC any child with suspected serious illness, i.e., diarrhoea with some or severe dehydration, pneumonia, ear or throat infection, repeated episodes of fever, loss of appetite, or failure to respond to feeding. Self referral will also be encouraged and entertained at any hour of the day. The child will be evaluated and managed accordingly by any of the investigators (during day time) or the on-duty physician (at night). Readmission to the hospital and the NRU will depend upon existing CRSC guidelines. Any child readmitted to the NRU will not be re-enrolled into the study, but will maintain the pre-readmission status as a study subject. The physician will also record in the precoded form diagnosis, treatment, duration, and outcome of any severe illness including relapse of severe malnutrition or septicemia.

Upon attaining the target WH of more than 80%, the children will be advised to attend the nutritional follow-up clinic (NFU) of the CRSC at monthly intervals until they achieve a WH >90%. During the visits to the NFU, a health worker will discuss the overall condition of the child, the change in weight and the child's diet with the mother. Health and nutrition education of the mothers or caretakers will be reinforced.

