### **Treatment B**

Children on treatment B will also stay in the NRU for a stabilisation period of 7 days during which their mothers or caretakers will have learnt preparation of khichuri and halwa and taking care of the children at home. Dietary therapy, micronutrient supplementation, training of mothers or caretakers, immunization, and anti-helminthic treatment will be the same as in treatment A. Thereafter, they will be discharged and advised to attend the NFU every week for one month and then at fortnightly intervals until they achieve an oedema-free WH >80%. If a child develops an acute illness or the general condition is not satisfactory at the time of discharge, then the discharge will be postponed till resolution of the illness. The protocol for follow-up will be the same as in treatment A, the difference being that the children will be

brought to the NFU by the parents. If a child fails to attend the NFU within 2 days of a specified follow-up day, a health worker will make a home visit, do the follow-up and reiterate the importance of bringing the child to the NFU for follow-up. The health worker, in course of her follow-up, will try to find out the reason(s) for defaulting. A previous study conducted at the NRU [12] to find out the cause of defaulting showed the principal reason to be the wrong perception of the parents that follow-up was not needed since the child was okay. Other reasons that came up during the previous study, and that will also be inquired during the follow-up visit by the health worker in this study, include: inability of the mother to come to the hospital alone, illness of the mother or child, distance, visit to village homestead, inability to leave other children at home alone, inability to afford the travel expenses, and death of the child.

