### **Treatment C**

Children on treatment C will remain admitted in the NRU until they have achieved an oedema-free WH >80%, and have a good general condition. This will typically involve a stay in the NRU for 15-25 days. The standardized feeding schedule will be followed and micronutrient supplements provided until discharge (refer to treatment A). Training of mothers or caretakers, immunization, and anti-helminthic therapy will be the same as in treatment A, except that in this treatment schedule the mothers or caretakers will receive more educational lessons due to their longer stay in the NRU. Morbid conditions occurring during rehabilitation, including diarrhoea, pneumonia, or septicemia will be recorded in precoded forms. After being discharged from the NRU, the children in this group will be advised to attend the NFU at intervals of two weeks for one month, and then at monthly intervals until they achieve a WH >90%. The entire family will be encouraged to come for the follow-up visit during which preparation of khichuri and halwa will be demonstrated to the mothers and then served to all members. Health education of the mothers or caretakers will be reinforced. Iron supplementation will be continued for 2 months in usual doses. Intercurrent illnesses such as diarrhoea or pneumonia will be treated.

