### **Outcome Measures**

- Time to recovery (achievement of WH 80%, oedema-free), in days
- Rate of weight gain, in g/kg per day calculated from lowest weight to discharge weight
- Speed of loss of oedema, in days
- Failure to respond
- Morbidity, in number and duration of episodes over equal periods of follow-up for both groups
- Mortality
- Cost of treatment

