1. Children will be admitted to the nutritional rehabilitation unit (NRU) only upon resolution of acute illness(es) including diarrhoea, pneumonia, gross electrolyte imbalance, and septicemia. Criteria of resolution of acute illnesses have been defined in the protocol (attached herewith). Therefore, during the 7 days of stay in the NRU, the two groups of study children will be free of any acute illness that might pose a risk. However, if a child develops an acute illness during stay in the NRU or if the general condition is not satisfactory at the time of discharge, then the discharge will be postponed till resolution of the illness. This pre-condition to discharge is part of the management protocol.
2. In 41 severely malnourished children with bilateral pedal oedema consecutively admitted to our NRU for management, the median period of time taken for resolution of oedema was 7 days (mean  $\pm$  SD, 7.0  $\pm$  3.7 days). Therefore, by the time (by day 7 in our proposed study) children will be discharged from the NRU, most of them will be oedema-free.
3. In the oedematous form of protein-energy malnutrition, there is no simple association between mortality and the severity of weight loss, whereas the serum albumin concentration at admission is strongly associated with mortality (1). In a retrospective multivariate analysis seeking to find out the predictive markers of death in a cohort of 1129 children in Central Africa, serum albumin concentration, and not oedema, was found to be the best predictor of subsequent risk of dying (2). It was concluded from the study results that an isolated clinical sign such as oedema is not enough to detect severely malnourished children with a high risk of dying.

4. In a conceptually identical type of study done in Dhaka, the median period of time taken for resolution of oedema by severely malnourished children managed at home was 19 days, compared to 11 days by those managed on an inpatient basis (3). Mortality, however, was the same in both the groups, 3.5%.

In consistence with the pre-condition to discharge built within the study protocol and the literature cited, we feel that discharging some children with oedema after 7 days of NRU stay will not pose an additional risk. By the time the children are discharged, the mothers/caretakers will have learnt about proper care taking, feeding and identification of the acutely ill child.

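### Failure to respond is defined only by follow-up visits, which the hospital arm does not have before recovery, so this outcome cannot be compared between home and hospital care

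*Protocol*

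**What the plan says.** Outcome Measures lists "Failure to respond" as one of seven outcomes. Specific Aims places it among the outcomes to be compared between home-based and hospital-based care and says that its definition is in the methods section. Data Analysis compares outcomes within and between groups from enrollment to discharge.

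The methods section holds one definition, under Treatment A, Follow-up: "Lack of weight gain for two consecutive visits will constitute failure to respond". The arms then differ as follows.

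- **A:** after seven days in the nutritional rehabilitation unit (NRU), "a health worker will visit the child every week for one month and then at fortnightly intervals".
- **B:** children are "advised to attend the NFU every week for one month and then at fortnightly intervals until they achieve an oedema-free WH >80" per cent, and "The protocol for follow-up will be the same as in treatment A". The failure rule therefore carries over to B.
- **C:** "Children on treatment C will remain admitted in the NRU until they have achieved an oedema-free WH >80" per cent. On duration: "This will typically involve a stay in the NRU for 15-25 days". The Treatment C text refers back to A for feeding, micronutrients, training, immunization and anti-helminthic treatment, but not for follow-up or the failure rule. It gives no weighing interval in the NRU. Clinic visits begin only after discharge, two weeks apart for a month and then monthly.

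On oedema, Enrollment Criteria admit oedematous children. The reply to the Ethical Review Committee reports that in 41 such children "the median period of time taken for resolution of oedema was 7 days" (mean 7.0, SD 3.7), and accepts that some will go home with oedema.

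**The concern.** An outcome meant to compare arms needs a rule that can be applied to every arm. This one is counted in visits, and visits exist in A and B but not in C during the period that matters. Whoever analyses the trial must either report no failures in C or devise a rule for C afterwards, in a trial that cannot be blinded (a referee comment attached to the protocol says so). In both cases the chi-square comparison would partly measure how often children were weighed.

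Two further features affect the meaning of a failure within A and B. The same child needs a longer run without gain once visits become fortnightly. And a child losing oedema fluid can show no gain while responding to treatment. The rate-of-weight-gain outcome guards against this by starting from the lowest weight; the failure rule has no such protection.

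**Working it through.** There is no stated figure to reproduce, so the check has four parts.

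**1. Can the rule be applied in each arm?** The clock starts at randomization, when children enter the NRU.

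| Arm | Visits before oedema-free WH >80% | Rule usable before recovery? |
|---|---|---|
| A | weekly, then fortnightly, after day 7 | yes |
| B | same intervals, at the clinic | yes |
| C | none (inpatient, typically 15-25 days) | no |

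C's first two post-discharge intervals end 14 + 14 = 28 days after the child has already recovered, so they cannot define failure during rehabilitation.

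**2. Length of the window in A and B.** Taking one month as 28 days, visits fall at days 7, 14, 21, 28, 42, 56 and 70 after NRU discharge, with the discharge weight at day 0. If the rule means two successive intervals without gain:

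- days 0-14, 7-21 and 14-28: 14 days
- days 21-42 (across the change): 21 days
- days 28-56 and 42-70: 28 days

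If it means no gain between two adjacent visits, the windows are 7 and then 14 days. On both readings the window doubles. The first full 28-day window closes on study day 7 + 56 = 63, well after the 35 days to recovery that Sample Size assumes for outpatient follow-up, so it concerns only slow recoverers.

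**3. How much does the weighing interval matter?** This is an illustration. The model is weight in g/kg = gain x days + normal error, with 50,000 simulated children who all truly gain at the same rate. The error SD of 10-20 g/kg is an assumption; the gains of 4 and 8.4 g/kg/day are those in Sample Size; 1 g/kg/day is an assumed slow responder. The event is two successive changes of zero or less.

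| True gain (g/kg/day) | Four weekly intervals | Every 3 days over 28 days | Daily over 18 days |
|---|---|---|---|
| 8.4 | 0% | 0-5% | 36-74% |
| 4 | 0-1% | 7-33% | 75-89% |
| 1 | 11-23% | 56-68% | 93-95% |

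For the lengthening window in A and B, at 1 g/kg/day one pair of weekly intervals gives 3.6-8.5% and one pair of fortnightly intervals gives 0.4-3.7%.

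**4. Oedema.** The reply to the Ethical Review Committee puts oedematous children at one-third of severely malnourished admissions. If enrolment mirrors that, 75 x 1/3 = 25 per arm. With a median of 7 days, about 25 x 0.5 = 12 still have oedema at the day-7 discharge. By day 14, assuming normality, z = (14 - 7.0)/3.7 = 1.89, an upper tail of about 3%, or 25 x 0.03 = 0.7 children. The same reply cites an earlier Dhaka study with a median of 19 days at home against 11 as inpatients. If that applied here on the same clock, more than half (over 12) would still have oedema at day 14. The number affected is thus uncertain, from under 1 to over 12 per home arm.

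**The case against.** The strongest counter-case has several parts.

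- **Importance.** This is one of seven outcomes. Sample size rests on weight gain, time to WH >80% and cost. Time to recovery and rate of gain are defined without visits and capture much of the same response. A and B share one schedule. All of this stands, and it limits the severity.
- **A statistical analysis plan could supply the definition.** This does not answer the point. Specific Aims says that the methods section gives the definition, and the one given cannot be used in the comparator arm. Weights on matching days must also be collected, so wording added after the data are in may come too late.
- **The daily-weighing percentages.** A reader might infer that a large share of C children would be labelled failures. The protocol does not support that: it states no daily weighing, does not call a ward weighing a visit, and gives no measurement error. The simulation also gives every child the same gain, although Sample Size reports an SD of 7.3. Only the sensitivity to weighing interval survives.
- **Oedema.** A reader might take the 12 children per arm as misclassified failures. They are not: a child must show no gain over the whole window, and tissue gain offsets fluid loss. The Ethical Review Committee had also asked for oedematous children to be excluded. The text at hand does not show how that ended, and the oedema part falls away if they were.
- **Withdrawal.** A reader might infer that failing automatically removes a child from the study. Data Analysis only says how data from children withdrawn for that reason are used. The Follow-up text makes the consequence referral and keeps readmitted children as study subjects. What stands is that the two sections leave the matter unclear.

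**Conclusion.** The point holds for the home-versus-hospital comparison of failure to respond. As written, C's rate is either zero by construction or depends on an unstated weighing interval, so a difference from A or B on this outcome could not be interpreted. That conclusion rests on the document text alone. The simulated percentages show only that the rate is sensitive to the interval and are not a forecast. The lengthening window and the silence on oedema are secondary: they blur what a failure means within A and B, by an amount that the documents do not allow one to fix. A versus B remains comparable, and the sample size is untouched. Severity: should be fixed.

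**What to change.** For the analysis, define failure to respond in calendar time from randomization, identically in all three arms:

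1. The investigators set the interval. Windows run until recovery or the end of follow-up, with no gap for late failures.
2. Allow a tolerance around the scheduled days, because A and B visits run from a discharge that can be postponed.
3. Take or extract C's NRU weights at the same spacing as the A and B visits.
4. Say how persisting oedema counts, for example as its own component or through a sensitivity analysis. Do not start the count only at the first oedema-free weight: a child whose oedema never clears could then never fail, and the start would depend on a post-randomization event that may differ by arm.
5. Keep the visit-based rule, unchanged, only as the home and clinic referral trigger.
6. Reconcile Treatment A, Follow-up with Data Analysis on whether a child who fails to respond stays in the study or is withdrawn. That choice belongs to the investigators.

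The cost is one reworded definition and confirmation that C weights exist on matching days. It should be settled before enrolment, since weights not taken cannot be recovered.
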